4.2.11. Last treatment administration date, End of Study date and Period definitions

The last treatment administration date will be defined as the date from the treatment termination of main period eCRF page. If this date is missing, the last date with a drug intake in eDiary strictly inferior to Month 6 date or the last date with a drug intake in eDiary available if the subject discontinued will be used.

For each 28-day period prior to Month X (except Month 6), the end of the period will be defined as the Month X visit date. If subject discontinued prior to Month X, the end of the period will be the date from the treatment termination of main period eCRF page or the last date with a drug intake in the eDiary if missing. If the subject missed the Month X visit (but did not discontinued), the subject might still have filled the diary during that time: the theoretical Month X date will be used to define the end of the 28-day period. The theoretical Month X is defined with respect to Day 1 as Month X= Day 1+ 28*X. Theoretical visits are presented in Table 3 of Section 4.2.9.

For the 28-day period prior to Month 6, the end of the period will be defined as the last treatment administration date.

The end of study date will be Month 6 date -1 day for subjects entering the Extension, and the last assessment date defined as last eCRF (excluding AE and CM end dates) or eDiary date in main study or main Follow-up for subjects not entering the Extension. This will not necessarily be the same date as last assessment date as recorded in the eCRF.

Note: For summaries by visit (efficacy or safety), the Month 6 assessments will be included in the main study analyses. For Adverse Events, Concomitant Medications and Daily diaries, data collected on Month 6 date will be part of the extension for subjects entering the extension study, and be part of the Follow-up period for subjects entering the main study follow-up period.

The main treatment period will be defined as Day 1 up to (Month 6 date -1) or treatment discontinuation date.

The main follow-up period will be defined as the Month 6 date or (treatment discontinuation date+1) up to the end of study date (for subjects who entered the follow-up).

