The analysis of the proportion of subjects reporting no analgesic use for EAP, and the proportion of subjects reporting no opiate use for EAP during the preceding 4-week period at Month 6 (last 28 days prior to and including last treatment administration date) will be conducted using a logistic regression model, with treatment group as the main effect (three values).

In addition to analgesic use for EAP as collected in the eDiary, concomitant medications in the study will be reviewed and medications to be considered as analgesic use for endometriosis associated pain will be confirmed by the Sponsor and be provided in an excel file prior to Database Lock. They may include any

Sponsor:	ObsEva		
Protocol:	18-OBE2109-003		
Document Version No.:	V5.0	Document Date:	13-JUN-2022

medication with the ATC codes from WHO drug dictionary version March 2016 as listed in Table 6 in Section 4.6.2.2.

In addition to analyzing the absence of analgesic use for EAP, the amount used for each 4-week period up to Month 6 will be summarized as a continuous variable, including the change from baseline. This analysis will be based on e-diary data only, as subjects did not record opioid intake in the concomitant medication page on a tablet-by-tablet basis.

As it is likely that more than one opioid will be used (opioid analgesic may be different depending on countries), the amount of opioid used will be converted to morphine milligram equivalents (MME) in order to better quantify the actual amount of opioids used by subjects.

For countries (Spain, Hungary, France, Czech Republic) where several opioids with different MME were allowed, the data collected in the e-diary is not sufficient to determine exactly which opioid was used and what the MME is. The MME will be derived as the average of possible MME of the allowed opioids in the country.

No opioids are allowed in Ukraine. Subjects from Ukraine will therefore be excluded from the summary in MME. If some opioids are nevertheless recorded for subjects from Ukraine, they will not be considered for the summary in MME, as the conversion in MME would be unknown. Those opioids records will however be considered for other analgesic use analyses not requiring conversion in MME.

The baseline amount of analgesic used will be computed by averaging the amount used during the two baseline menstrual cycles.

Conversion to MME by country is described in Table 7.

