4.6.4. Additional Secondary Endpoints

All additional efficacy endpoints will be summarized by descriptive statistics for each treatment group, for each time point, including summaries of change from baseline when applicable. Individual linzagolix versus placebo treatment group comparisons will be made.

In general, between group comparisons for continuous endpoints will be analyzed via analysis of (co)variance. Between-group comparisons for binary endpoints will be analyzed via logistic regression. Between-group comparisons for ordinal categorical data will be analyzed using a Mantel-Haenszel test, or using Koch's method when there is also a baseline covariate.

As described in section 4.2.5 additional secondary endpoints will use Bonferroni correction for p-values of comparison of treatment groups at each visit. The analyses do not form part of the fixed-sequence strategy being used for the ranked secondary endpoints and will not be fully controlled for an overall type I error rate.

Values for all endpoints that are collected daily using the eDiary (from Section 4.6.4.1 to Section 4.6.4.18) will be based on the 28 calendar days immediately prior to and including the day of the corresponding visit or prior to and including the last treatment administration date for Month 6, or the 28 calendar days immediately prior to and including the last dose date for subjects who discontinue treatment prior to the visit in question (or fewer if treatment is stopped less than 4 weeks after first dose date), in order to estimate the treatment effect while under treatment. The last 28 days on treatment will be used at all subsequent scheduled visits for those discontinued subjects. Descriptive summaries for each 28-day period will be performed in two ways however:

- Once including only values of 28 days prior to Month X, i.e. using the last 28 days prior to Month X eCRF visit date for subjects who have not discontinued up to that month. If subjects discontinued prior to Month X the corresponding value will be missing from the summary at Month X;
- Once applying the while on treatment strategy, i.e. using the last 28 days prior to Month X eCRF visit date for subjects who have not discontinued up to that month, and for subjects who discontinued prior to Month X, the last 28 days prior to treatment discontinuation will be used. For all subsequent timepoints (Month X+1, etc.) the same last 28 days prior to treatment discontinuation will be used.

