4.6.4.5. Change from baseline to each scheduled assessment in mean daily dyspareunia scores

Sponsor:	ObsEva		
Protocol:	18-OBE2109-003		
Document Version No.:	V5.0	Document Date:	13-JUN-2022

reported during the previous 4-week period on the dyspareunia VRS

The actual value and change from baseline in mean daily dyspareunia scores will be summarized as a continuous variable for each 28-day period. An analysis of covariance will be performed for each period.

Subjects not sexually active for reasons other than endometriosis will have missing values for the corresponding 4-week periods. Subjects not sexually active for reasons other than endometriosis at baseline will be excluded from the analysis.

4.6.4.6. Change from baseline to each scheduled assessment in mean daily dyschezia scores reported during the previous 4-week period assessed on the dyschezia NRS

The actual value and change from baseline in mean daily dyschezia scores will be summarized as a continuous variable for each 28-day period. An analysis of covariance will be performed for each period.

4.6.4.7. Change from baseline to each scheduled assessment in non-opioid, opioid and combined analgesic use for EAP during the previous 4-week period based on pill count in the eDiary

Non-opioid, opioid and combined analgesic use for EAP will be measured using the mean of daily pill count collected in the eDiary over each 28-day period. For non-opioid and combined analgesic use, descriptive summary (actual values and changes from baseline) and analysis of covariance for each period will be performed. Due to a low number of subjects using any opioids, opioids use will not be analyzed as a continuous variable, only a listing with by subject opioid use mean daily pill count will be provided.

The number and percentage of subjects reporting no analgesic use for EAP, and the proportion of subjects reporting no opiate use for EAP at baseline and during the preceding 4-week period at Month 3 (last 28 days prior to and including last treatment administration date) will be presented. The proportion of subjects with no analgesic use for EAP, and with no opiate use for EAP will be conducted using a logistic regression model, with treatment group as the main effect. For these proportions, in addition to eDiary analgesic use, data from the concomitant medication page will be used, as described in Section 4.6.3.6.

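### SAP 4.6.4.7 ends the Month 3 window for the no-analgesic and no-opiate proportions at the last treatment date, so as written the Month 3 analysis repeats Month 6

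*SAP*

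**What the plan says.** SAP 4.6.4.7 calls for the number and percentage of subjects with no analgesic use, and with no opiate use, at baseline and in the four weeks before Month 3, followed by a logistic regression on treatment group. The post-baseline period is specified as "at Month 3 (last 28 days prior to and including last treatment administration date".

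The closing date is a defined term. SAP 4.2.11 states: "The last treatment administration date will be defined as the date from the treatment termination of main period eCRF page". If that date is missing, the fallback is the last recorded intake before the Month 6 date, or the last available intake for a subject who discontinued.

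For the ranked Month 6 versions of the same two proportions, SAP 4.6.3.6 uses the same parenthesis: "at Month 6 (last 28 days prior to and including last treatment administration date".

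The general rules differ by visit. SAP 4.2.11 says "For each 28-day period prior to Month X (except Month 6), the end of the period will be defined as the Month X visit date", and separately "For the 28-day period prior to Month 6, the end of the period will be defined as the last treatment administration date". The opening of SAP 4.6.4 sets the window for the daily eDiary endpoints in 4.6.4.1 to 4.6.4.18 as the 28 days "immediately prior to and including the day of the corresponding visit or prior to and including the last treatment administration date for Month 6", with the last dose date used for subjects who discontinue before the visit in question.

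**The concern.** The specific text for this endpoint ties a Month 3 result to a date that, for most subjects, falls around Month 6. A programmer who follows it would produce a table labelled Month 3 that contains Month 6 data. The error would be hard to spot, because the percentages and odds ratios would look plausible.

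Month 3 is the primary time point, and stable or decreased analgesic use is part of the co-primary responder definition. Readers are likely to look to the Month 3 analgesic-free and opiate-free rates when interpreting the primary result. Agreement between the Month 3 and Month 6 rates could also be misread as an early effect that persisted.

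**Working it through.** **Inputs**

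- Visit day formula (SAP 4.2.11): "The theoretical Month X is defined with respect to Day 1 as Month X= Day 1+ 28*X".
- Theoretical visit days (SAP Table 3): Month 3 = Day 85, Month 6 = Day 169.
- Last dosing day for a completer (protocol 11.2): the day before the Month 6 visit, nominally 169 − 1 = Day 168.
- A 28-day window ending on day E covers days E − 27 to E.

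**Reproducing the plan's visit days**

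- Month 3: 1 + 28 × 3 = 85.
- Month 6: 1 + 28 × 6 = 169.

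Both agree with Table 3.

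**Windows for a completer**

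| Rule | End day | Window |
|---|---|---|
| Month 3, general rule (4.2.11 and 4.6.4) | 85 | 85 − 27 = 58, so Days 58–85 |
| Month 3, as written in 4.6.4.7 | 168 | 168 − 27 = 141, so Days 141–168 |
| Month 6 (4.6.3.6) | 168 | Days 141–168 |

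The second and third rows are identical. The first and second share 0 of 28 days, with 141 − 85 − 1 = 55 days between them.

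**Does visit timing rescue it?** No.

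- With Month 3 three days late and Month 6 three days early, the proper Month 3 window ends on Day 88 and the literal window starts on Day 138.
- With shifts of 14 days, the corresponding days are 99 and 127.

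**Subjects who discontinue** (last dose on day L, Month 3 visit at Day 85)

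- Stopping before Month 3: every rule ends the window at L, so the windows agree.
- Stopping between Month 3 and Month 6: the literal window ends at L and so equals the subject's Month 6 window. Its overlap with Days 58–85 is 28 − (L − 85) days until that reaches zero:

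| Last dose day L | Literal window | Days shared with 58–85 |
|---|---|---|
| 90 | 63–90 | 23 |
| 100 | 73–100 | 13 |
| 112 | 85–112 | 1 |
| 113 or later | starts at Day 86 or later | 0 |

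Taken literally, then, the Month 3 and Month 6 windows coincide for every subject, not only for completers.

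**Is anything else different between the two analyses?** The model is the same (logistic regression with treatment as the main effect), and 4.6.4.7 takes its concomitant-medication data as in 4.6.3.6. With the same window, model and data sources, the post-baseline results would be the same.

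**Was it a deliberate change?** Nothing suggests so. The V3.0 entry in the SAP Section 5 table describes adding these proportions at baseline and Month 3. The departure from the protocol declared in Section 5 concerns only the Month 6 window. The wording looks as though it was carried over from 4.6.3.6, where it is correct.

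**The case against.** The best defence is that the SAP elsewhere gives the right answer. The sentence itself names Month 3, the window rule in 4.6.4 covers 4.6.4.7 by section range, and 4.2.11 ends every window other than Month 6 at the visit date. A programmer who worked from those rules would obtain Days 58–85. On this view the defect is a stray parenthesis, and the wrong result follows only if it is read literally.

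That is fair as a description of how the error probably arose, and it means the wrong result is not certain to be produced. It does not remove the problem. The endpoint-specific text is explicit and uses a defined term, and specific text is often what governs programming. A plan with two incompatible windows for one analysis should not leave the choice to the programmer.

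The point about importance also stands in part. The Month 3 proportions were added in the SAP and lie outside the fixed sequence. SAP 4.6.4 says the additional secondary analyses are not fully controlled for type I error. The SAP also notes that few subjects used opioids, so the no-opiate half may carry little information. This limits the weight of the finding but not its correctness.

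**Conclusion.** The concern holds. As written, the Month 3 window is the Month 6 window: for completers it shares no days with the intended period, and for subjects who stop between the two visits it moves with their last dose. Only subjects who stop before Month 3 get the intended window.

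The day counts assume nominal visit dates and dosing up to the day before the Month 6 visit. For completers, the lack of overlap survives visit shifts of up to 14 days.

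The reach is limited to the two Month 3 proportions and their logistic regressions. The co-primary endpoints have their own Month 3 window, and the ranked Month 6 endpoints are correctly specified. It should be corrected, but it does not threaten the trial's main conclusions.

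**What to change.** In SAP 4.6.4.7, replace the parenthesis so that the window is the 28 days up to and including the Month 3 visit date, or up to and including the last treatment administration date for subjects who discontinue before Month 3. Add a cross-reference to 4.2.11, so that a subject who misses the visit without discontinuing uses the theoretical Month 3 date. This applies the SAP's own general rule.

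The cost is one sentence, plus a check that the program and any output already produced use the corrected window. No new data are needed.

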4.6.4.20. Change from baseline to each scheduled assessment in the Health-Related Productivity

Sponsor:	ObsEva		
Protocol:	18-OBE2109-003		
Document Version No.:	V5.0	Document Date:	13-JUN-2022

Questionnaire (HRPQ) scores

The Health-Related Productivity Questionnaire (HRPQ) is a validated, 9-item, self-reported questionnaire that has been used to evaluate health-related productivity.

The HRPQ includes items on employment status; effect of health issues or treatment on working scheduled hours (absenteeism); effect of health issues or their treatment on work output (presenteeism); effect of health issues or their treatment on planned hours of household chores; effect of health issues or their treatment impact work output for household chores actually performed; how long since health issues developed; and effect of health issues on life.

The questionnaire follows a skip pattern so that subjects can answer only the items applicable to them according to whether they work outside the home (eg, full- or part-time employment). Two subject groups are defined: employed and household (employed and not employed, combined).

See Appendix C in Section 7.3 for HRPQ Scoring.

At Day 1, the following will be summarized:

- Employment status,
- Time since symptoms developed,
- Number of subjects and time for which Endometriosis symptoms or its treatment(s) forced to work part-time when wanted to work full-time,
- Number of subjects and time for which Endometriosis symptoms or its treatment(s) kept from having a job when wanted to work full-time,
- Number of subjects and time for which Endometriosis symptoms or its treatment(s) kept from having a job when wanted to work part-time.

The following scores (actual values and changes from baseline) will be summarized at each visit (Day 1, Month 1, Month 2, Month 3, Month 4, Month 5, Month 6):

- For "Employed" group:
 - Number of hours of work lost due to absenteeism ("How many hours of work did you miss because of illnesses/treatments the last week?")
 - Number of hours of work lost due to presenteeism ("For the hours that you did work during the past week, how did illnesses/treatments impact your work output?")
 - o Total number of hours of work lost
 - Percent of scheduled work lost due to absenteeism (Number of hours lost/Number of scheduled hours*100)

Sponsor:	ObsEva		
Protocol:	18-OBE2109-003		
Document Version No.:	V5.0	Document Date:	13-JUN-2022

- Percent of scheduled work lost due to presenteeism (Number of hours lost/Number of scheduled hours*100)
- Percent of scheduled work lost in total (Number of hours lost/Number of scheduled hours*100)
- For "Household" group:
 - Number of hours household work lost due to absenteeism ("How many hours of work did you miss because of illnesses/treatments the last week?")
 - Number of hours household work lost due to presenteeism ("For the hours of household chores that you did during the past week, how did illnesses/treatments impact your work output?")
 - Total number of hours of household work lost
 - Percent of scheduled household work lost due to absenteeism (Number of hours lost/Number of scheduled hours*100)
 - Percent of scheduled household work lost due to presenteeism (Number of hours lost/Number of scheduled hours*100)
 - Percent of scheduled household work lost in total (Number of hours lost/Number of scheduled hours*100)

The change from baseline in the percentage of scheduled work lost due to absenteeism/presenteeism/total for employed and household groups will be analyzed with an analysis of covariance.

4.6.4.21. Number of non-study endometriosis related health visits, number of days in hospital and type of procedures performed based on Health Resource Utilization Questionnaire (HRUQ) at each scheduled assessment

The number of non-study endometriosis related health visits, number of subjects by type of clinician/clinic visit, number of subjects by type of therapeutic procedures, and number of nights spent in hospital will be summarized at each visit (Day 1, Month 1, Month 2, Month 3, Month 4, Month 5, Month 6). In case of many clinician/clinic types and therapeutic procedures, types may be regrouped for the descriptive summaries.

The change from baseline of number of non-study endometriosis related health visits and number of nights in hospital will be analyzed with a negative binomial model, including baseline as a covariate. The estimated least square means treatment differences along with 97.5% CI will be provided.

Sponsor:	ObsEva		
Protocol:	18-OBE2109-003		
Document Version No.:	V5.0	Document Date:	13-JUN-2022

4.6.4.22. Change from baseline to each scheduled assessment in the Physician/Subject Surgery Intention Question (PSIQ/SSIQ)

The PSIQ/SSIQ answers will be summarized as continuous at Day 1 and Month 6. Comparison between treatment arms at Month 6 will be done using analysis of covariance.

4.6.4.23. Change from baseline to each scheduled assessment in the PROMIS Fatigue – Short Form 6a

The PROMIS Fatigue Short Form 6a is composed of 6 items on 5-point scales (1-5). The total score is measured as the sum of answers of each item and will range from 6 to 30. The higher the total score, the more severe the symptom. Missing data will not be imputed.

Each item will be summarized by category at each visit (Day 1, Month 1, Month 3, Month 6). The total score will be summarized as a continuous variable.

An analysis of covariance will be performed on the total score.

4.6.4.24. Change from baseline to each scheduled assessment in the EuroQoL 5-Dimension 5-Level (EQ-5D-5L) questionnaire

The EuroQoL 5-dimension questionnaire (EQ-5D) is a self-administered, generic utility instrument developed by the EuroQoL Group in 1990. The EQ-5D consists of 2 parts, a descriptive system of 5 dimensions and a 20-cm vertical visual analogue scale (VAS) with endpoints 0 and 100. It is collected by the subject in the eDiary at Day 1, Month 1, Month 3, Month 6.

The descriptive system includes five single-item dimensions: mobility, self-care, usual activities, pain/discomfort, and anxiety/depression. Subjects must choose between five levels of difficulty (from 1 to 5) in accomplishing tasks in each dimension. The health states will be described in terms of five-digit numbers based on the answers to each of the five questions. The states will then be converted to a single index score using the TTO (Time Trade-Off) method. The TTO method has been chosen since this is the only one available for the United States (US) and also because for economic studies where cost utility analysis is anticipated, most health economists are recommending a value set that has been derived using a choice-based method. An index score based on the individual dimensions will be calculated using a scoring algorithm (see Reference document EQ-5D-5L_UserGuide_2015.pdf) and the US Index from Crosswalk value set downloaded from the EuroQol website.

Sponsor:	ObsEva		
Protocol:	18-OBE2109-003		
Document Version No.:	V5.0	Document Date:	13-JUN-2022

In the present study, the available US-specific scoring will be used (see Appendix D in Section 7.4. how to compute EQ-5D-5L crosswalk index values with SAS using the United States value set as an example).

Answers to each dimension will be summarized by category at each visit. The index value and VAS Score will be summarized as continuous variables (actual values and changes from baseline). Index value and VAS Score will be analyzed via an analysis of covariance

4.6.4.25. Response at each scheduled assessment according to Patient Global Impression of Change (PGIC) (and Post-treatment Patient Global Impression of Change, PPGIC)

Responses to the Patient Global Impression of Change questionnaire range from 0- Very much worse to 6-Very much improved. Responses will be summarized by category at each visit (Month 1, Month 2, Month 3, Month 4, Month 5, Month 6). A generalized linear model analysis for ordinal data will be performed. Odds-ratio and 97.5% confidence intervals estimates of having higher ordered responses categories, of each treatment group versus Placebo will be presented.

SAS Code (may be updated at analysis stage to fit the data): Generalized Linear Model for Ordinal Data Proc genmod data=dataset order=internal descending ;

Freq count; Class treatment ; Model pgic=treatment / dist=multinomial link=clogit; Estimate `logor 75 vs pbo' -1 1 0 / exp alpha=0.025 ; Estimate `logor 200 vs pbo' -1 0 1 / exp alpha=0.025 ; Ods output estimates=estimates ; Run;

4.6.4.26. Change from baseline to each scheduled assessment in the monthly PGIS (mPGIS) score

Responses to the Patient Global Impression of Severity range from 0- No symptoms to 4-Severe. Responses will be summarized by category at each visit (Day 1, Month 1, Month 2, Month 3, Month 4, Month 5, Month 6). A generalized linear model analysis for ordinal data will be performed. Odds-ratio and 97.5% confidence intervals estimates of having higher ordered responses categories, of each treatment group versus Placebo will be presented.

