10.3.3.7 Patient Global Impression of Severity - monthly recall (mPGIS)

At each study visit from Day 1 to the end of the follow-up period, the subject will be asked to evaluate the severity of her endometriosis symptoms over the past 28 days using a 5-point scale with the following possible answers: no symptoms, very mild, mild, moderate, severe (see Appendix J).

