⁵ If endometrium thickness in TVUS is \leq 5 mm, no endometrial biopsy will be necessary.

Page **21** of **127**

⁶ Overnight fasting is required.

⁷ PK samples should be taken after the ECG and before the daily dose of IMP, except on Day 1 when the PK sample should be taken at least 1.5 h after the IMP administration.

Sponsor:	ObsEva		
Protocol:	18-OBE2109-00	3	
Document Version No.:	V5.0	Document Date:	13-JUN-2022

Schedule of study assessments – Screening and Trea	atment Periods								
Timing ¹	Screening Period	Sereening Period Treatment Period							
	(up to 3 months ²)	Day 1	M1	M2	M3	M4	M5	M6	
Previous/concomitant medication	x	X	X	X	X	X	X	X	
Contraceptive dispensing and counselling	x	X	X	X	X	X	X	x	
Permitted analgesic prescribing/dispensing	x	x	x	x	x	x	x	x	
Vitamin D and calcium dispensing		x	x	x	x	x	x	x	
Subject eDiary completion training/check	x	X	X	X	X	X	X	x	
IMP accountability			x	X	x	X	x	x	
Dispense study drug		X	x	X	x	x	x		
Dispense ABT		x			x				

 Sponsor:
 ObsEva

 Protocol:
 18-OBE2109-003

 Document Version No.:
 V5.0

 Document Date:
 13-JUN-2022

Schedule of study assessments – Screening and Tro	eatment Periods	1						
	Screening Period	Treatment Period						
Timing ¹	(up to 3 months ²)	Day 1	M1	M2	M3	M4	M5	M6
EHP-30, EQ-5D-5L and PROMIS ⁸		X	X		X			X
mPGIS, PGIC, HRUQ and HRPQ		x ⁹	X	X	X	X	x	X
Specific monthly severity questions ⁸		x			x			x
SSIQ and PSIQ ⁸		x						x
АМН		x						
E2, LH, P4		X	X	X	X	x	x	X
SHBG		X			X			x

⁸ ClinROs (Monthly dyspareunia question, PSIQ and HRUQ) will be administered to the subject by the site staff and the responses will be filled in the eDiary. ePROs (EHP-30, EQ-5D-5L, PROMIS, PGIS, PGIC, HRPQ and SSIQ, and specific monthly severity questions) will be filled in by the subject in the eDiary.

⁹ PGIC not done at Day 1.

Sponsor:	ObsEva			
Protocol:	18-OBE2109-003			
Document Version No.:	V5.0	Document Date:	13-JUN-2022	

Schedule of study assessments – Screening and Treatment Periods								
	Screening Period (up to 3 months ²)	Treatment Period						
Timing ¹		Day 1	M1	M2	М3	M4	M5	M6
Bone biomarkers		x			x			x
Question regarding treatment received								x

Sponsor:	ObsEva			
Protocol:	18-OBE2109-003			
Document Version No.:	V5.0	Document Date:	13-JUN-2022	

Table 2 Schedule of study assessments - Follow-up Period

Schedule of study assessments – Follow-up Period						
M1 FU	M2 FU	M3 FU	M4 FU	M5 FU	M6 FU	
x	x	x	х	х	x	
X	X	x	x	х	x	
X	x	x	x	x	x	
X		x			x	
					х	
					x	
					Λ	

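### SAP 4.6.4.26 calls mPGIS a change-from-baseline endpoint but specifies an ordinal model of the visit category with no baseline term, which is valid but gives up some power

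*SAP*

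**What the plan says.** SAP 4.6.4.26 is headed "Change from baseline to each scheduled assessment in the monthly PGIS (mPGIS) score". It codes the response first: "Responses to the Patient Global Impression of Severity range from 0- No symptoms to 4-Severe". Categories are then tabulated by visit, Day 1 included. The comparison between arms is one sentence, "A generalized linear model analysis for ordinal data will be performed", followed by its output: "Odds-ratio and 97.5% confidence intervals estimates of having higher ordered responses categories, of each treatment group versus Placebo will be presented". The section derives no change score, names no covariate and prints no code.

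Section 4.6.4.25 (PGIC), just before it, has the same two model sentences and the only code printed for this type of model: "Model pgic=treatment / dist=multinomial link=clogit". PGIC has no baseline; a footnote to the assessment schedule in SAP 2.4 says "PGIC not done at Day 1". mPGIS does have one, since protocol 10.3.3.7 has it asked "At each study visit from Day 1 to the end of the follow-up period".

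The parent section, SAP 4.6.4, sets a general rule for ordinal data: a Mantel-Haenszel test, or "using Koch's method when there is also a baseline covariate". Protocol 13.5.4 has the same rule. SAP 4.2.4 says that covariate adjustments are described in the individual analysis sections. SAP section 5, which records changes to the planned analyses, mentions no departure for mPGIS.

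**The concern.** A treatment-only ordinal model suits PGIC, because the patient's rating is itself a change and nothing was measured at Day 1. Carried over to mPGIS, the same wording leaves the Day 1 rating in a descriptive table and compares severity at the visit without regard to where each woman started. That does not match the endpoint's name, the plan's own rule for ordinal data, or the neighbouring change endpoints, which use analysis of covariance or a negative binomial model with baseline as covariate.

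The stake is power on this endpoint, and clarity about what the odds ratio means. There is also a smaller trap in the shared wording. Both sections report the odds of a higher category. Higher is better on PGIC (6 is very much improved) but worse on mPGIS (4 is severe), so a benefit gives an odds ratio above 1 in one table and below 1 in the next. The SAP does not say so.

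**Working it through.** **1. The sections side by side.**

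| SAP section | Response modelled | Baseline collected? | Baseline in the model? |
|---|---|---|---|
| 4.6.2.1.2 co-primaries | responder yes/no | yes | yes, baseline pain score |
| 4.6.4.18 days in bed or lying down | count | yes | yes, negative binomial covariate |
| 4.6.4.25 PGIC | category 0-6 | no | none possible |
| 4.6.4.26 mPGIS | category 0-4 | yes | none named |

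Since 4.2.4 sends the reader to each analysis section for covariates, a programmer following 4.6.4.26 literally would leave Day 1 mPGIS out.

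**2. The plan's own figure.** The documents give no power or precision figure for mPGIS. The trial's sizing claim (SAP 4.1) is more than 95% power for both co-primaries at 150 per arm, with raw p-values doubled, that is, two-sided 0.025 per comparison. The limiting endpoint is NMPP, 18.8% against 42.1%:

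- SE = sqrt[(0.188×0.812 + 0.421×0.579)/150] = 0.0514
- z = 0.233/0.0514 = 4.53; power = Φ(4.53 − 2.24) = 98.9% (98.7% with pooled variance)
- DYS power exceeds 99.99% for either dose, so joint power is about 98.7%.

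The sizing claim reproduces. It says nothing about mPGIS, which needs its own check.

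**3. Effect of a Day 1 term.** A proportional-odds model was fitted to simulated trials, once with treatment only and once with treatment plus the Day 1 score (0-4) as a single linear term.

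- From the documents: three arms, 150 per arm, two-sided 0.025 per comparison.
- Assumed: Day 1 categories 0.1/1.9/10/50/38% (no symptoms to severe); placebo outcome 8/12/25/35/20%; both active arms shifted by 0.35 latent SD (unadjusted odds ratio about 0.55); latent correlation 0 to 0.6.
- 1,000 runs per setting. Relative efficiency is the squared ratio of the mean z statistics, adjusted over unadjusted.

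| Observed correlation | Log OR (SE), no baseline | Log OR (SE), with Day 1 | Power, no baseline | Power, with Day 1 | Relative efficiency |
|---|---|---|---|---|---|
| 0.00 | −0.595 (0.209) | −0.596 (0.209) | 73% | 73% | 1.00 |
| 0.17 | −0.599 (0.209) | −0.609 (0.209) | 75% | 77% | 1.03 |
| 0.30 | −0.594 (0.209) | −0.630 (0.210) | 74% | 78% | 1.11 |
| 0.43 | −0.589 (0.209) | −0.668 (0.212) | 73% | 83% | 1.24 |
| 0.52 | −0.592 (0.209) | −0.707 (0.214) | 72% | 86% | 1.36 |

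The standard error does not fall; it rises slightly. The gain comes from the log odds ratio moving away from zero once it is conditional on Day 1 severity.

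**4. Cross-check.** The linear-model formula 1/(1 − r²) gives 1.10 at r = 0.30, 1.23 at 0.43 and 1.37 at 0.52, close to the simulated values.

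**5. Validity.** With no treatment effect, rejection ran from 1.9% to 3.5% across both models and all settings, against a nominal 2.5% (Monte Carlo SE about 0.5 points). Neither model shows a type I error problem.

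**The case against.** The strongest reply is that 4.6.4.26 is silent rather than wrong. It prints no code; the treatment-only line belongs to PGIC and is marked as open to update at the analysis stage. The SAP is terse elsewhere too: for PROMIS and the surgery-intention questions it says analysis of covariance without naming the covariate. The general rule in 4.6.4 could be read as covering mPGIS already. This stands in part. A reader might infer that the SAP has deliberately chosen a treatment-only model, but the text does not say so. What it does is specify a model without a baseline term, at odds with its parent section, and 4.2.4 makes silence lean towards no adjustment.

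The gain may also be small. Entry requires moderate to severe pain, which could bunch Day 1 mPGIS in the top categories and weaken its correlation with later ratings. That stands, and is why the range starts at 1.00.

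Lastly, adding a Day 1 term still leaves the visit category as the response, so it does not literally analyse change. True, but comparing women with the same starting severity is the ordinal counterpart of the covariance analyses used for the sibling endpoints.

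**Conclusion.** The point holds as a low-impact inconsistency with a nearly free improvement. Followed as written, the model omits a baseline that is collected and that the plan's general rule would use. The price is between nothing and about 14 percentage points of power (72% against 86%) over observed correlations of 0 to 0.52. Those figures are illustrative: the correlation, the category distributions and the effect size are all assumed.

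Four stronger readings are tempting and should be resisted:

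- A reader might infer that the unadjusted estimate is less precise. In a cumulative-logit model it is not; its standard error is no larger, and what is lost is power.
- A reader might infer bias, or a test undermined by chance imbalance at Day 1. Randomisation keeps the unadjusted comparison valid.
- A reader might infer that the responder thresholds are affected, because mPGIS is one of their anchors. They come from a separate blinded analysis (SAP 4.6.1) that this model does not feed.
- A reader might treat mPGIS as the main global severity outcome. The documents list it last among the additional secondary endpoints, outside the fixed sequence and not fully controlled for type I error.

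**What to change.** In SAP 4.6.4.26, specify a cumulative-logit model with treatment (three groups) and Day 1 mPGIS as covariate, for example `model mpgis = treatment base_mpgis / dist=multinomial link=clogit`, and say how Day 1 enters (for example as a linear score 0-4). Koch's method, as 4.6.4 already provides, is an acceptable alternative. State that the odds ratio from the cumulative-logit model is conditional on baseline, and that higher categories mean worse severity, so a value below 1 favours linzagolix. If the unadjusted model is kept on purpose, retitle the endpoint as mPGIS severity at each visit and record the departure in section 5.

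The cost is one model term and no new data. There are three small downsides. The odds ratio becomes conditional rather than marginal. Women without a Day 1 mPGIS drop out of the model, so their number should be reported. The form of the baseline term is one more assumption.
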